7. TIME AND EVENTS

Potential participants will be screened via phone or REDCap surveys. If a potential participant qualifies after the screening survey, a visit to the UF campus CRC building will be scheduled.

Upon arrival at the CRC, informed consent will be reviewed, and the informed consent document will be signed. Following this enrollment, the participant will have vitals checked and will undergo an HbA1C fingerprick test, a urine pregnancy test, a physical exam, and a comprehensive medical history. If the participant still meets inclusion criteria, then screening accuracy is confirmed. Participants who are found to be screening failures will be told they are no longer eligible for the second part of the study and be given a gift card. For those that continue, blood will be drawn and sent to respective locations outlined in Table 1. Subsequently, the Pneumovax 23 vaccine will be administered. Following administration of the vaccine, four questionnaires will be administered; simultaneously while completing the forms, the

participant will be monitored for adverse side effects to the vaccine. Payment will be administered after the surveys, and the subsequent visit will be scheduled.

At the second visit 4-6 weeks following the first, blood will be drawn once more and distributed to the locations outlined in Table 1. After the blood draw, the participant will be compensated and thanked profusely for participating in the study. Completion of visit two marks the culmination of the study for that particular participant. Data analysis will ensue once 56 participants have progressed through the study. The events occurring in the study are outlined in Table 3.

Table 3. Proposed Schedule

	Events	Prior to Visit 1	Estimated Time (min)	Visit 1: Day 0	Visit 2: Wk 4-6
Screening	Contact with participants by phone or email	X	10		
	Set up REDCAP and chart for each participant	X	20		
	Screening via phone or REDCAP survey	X	10		
	Instructions email or phone call	X	10		
Visit 1	Informed Consent		20	X	
	Urine Pregnancy Test		10	X	
	A1C		5	X	
	Medical History		10	X	
	Physical Exam,		10	X	
	Waist/Hip Ratio		2	X	X
	Vitals		2	X	X
	Blood draw for CMP, CBC, and ESR		6	X	
	Pneumvax23 Vaccination		5	X	
	Blood draw for total IgG, serotypes, and cytokine assays		6	X	X
	Questionnaire Completion (4 surveys)		30	X	
	Instructions for next visit		5	X	
	Payment		5	X	X
	Total Time Per Visit (min)			114	20-30

Effect of Obesity on Immune Response to Pneumovax 23 (ROVE)

NCT02471014

April 17, 2017

Statistical Analysis Plan (SAP)

Clinicaltrial.gov Identifier: NCT02471014

Introduction:

Obesity has been correlated with higher mortality risk and is associated with a proinflammatory state. Obesity has also been associated with a lower immune response to various types of vaccination (e.g. influenza, hepatitis B, tetanus). As the prevalence of obesity increases, so does the need for a deeper mechanistic understanding of how obesity attenuates vaccination response. It is important to assess the effect of obesity on the immune response to vaccines. The pneumococcal polysaccharide vaccine (Pneumovax 23) is a safe method for stimulating an immune response and its effect on obesity has not been elucidated. As a growing population of obese individuals inevitably age and become susceptible to pneumococcal infections, it is important to consider how obesity may impact the efficacy of Pneumovax 23. We hypothesize that a chronically stressed immune system in obese individuals will be unable to respond as well to vaccination compared to individuals with a BMI between 22 and 25. We will utilize a prospective cohort design. We will also conduct various surveys to examine psychosocial factors that may influence the interaction between obesity and immune response to vaccination. We will also perform genotyping of STING to assess how it may influence the relationship between obesity and immune response to vaccination.

Study design:

This study is a prospective cohort study with two arms: (1) those with a body mass index (BMI) between 22 and 25 and (2) those with a BMI greater than or equal to 30 and a waist-to-hip ratio of at least 0.9 in males and 0.85 in females. Participants will have a baseline visit where they will receive a pneumococcal polysaccharide vaccine and a follow-up visit four-six weeks after.

Sample size calculation

The primary outcome measure for the power calculation was the number of positive pneumococcal titers using data from Wildes et al. (2019). This study included a range of BMIs under 30. By comparing the number of positive titers between those with a BMI < 25 and > 25, we expect that 23 evaluable obese participants and 23 evaluable normal weight participants will provide enough power for the study (see the distribution of positive titers below in Table 1) at a significance level of $\alpha = 0.05$ for a 2-sided t test at 80% power. We consider this estimation to be conservative, as we expect that having a greater separation of BMI values than Wildes et al. will provide greater power. The actual gain in power cannot be quantified.

Table 1. The distribution of positive titers amongst the 14 in Wildes et al. study was as follows:

BMI	5	6	7	8	9	10	11	12	Total
<25	1	2	0	2	2	1	4	2	14

>25	0	2	3	0	1	1	0	0	7
-----	---	---	---	---	---	---	---	---	---

Aims and objectives

The aim of this project is to investigate the effect of obesity on the immune system's ability to mount a protective immune response against the pneumococcal polysaccharide vaccine (Pneumovax 23).

Outcomes

Primary outcome: Vaccine response as measured by serotype-specific IgG antibody responses against the 23 pneumococcal serotypes (i.e., 1, 2, 3, 4, 5, 6B, 7F, 8, 9N, 9V, 10A, 11A, 12F, 14, 15B, 17F, 18C, 19A, 19F, 20, 22F, 23F, 33F)

Statistics:

When comparing between populations (ie. baseline characteristics table), normality was first assessed by the Shapiro-Wilk test, then followed by either an unpaired 2-sided t test or a Wilcoxon's signed-rank test for parametric data or nonparametric data, respectively. Chi-square tests determined differences in categorical data (i.e. sex, ethnicity). For our primary analysis, we will use an ANCOVA to test for differences in fold change titer levels across groups (nonobese and obese), controlling for sex and age. All hypothesis tests were 2-sided where a P value < 0.05 was considered significant.

To assess the role of the STING genotype, a secondary analysis will be done using 2-way ANOVA of the fold change in titer levels between the wildtype, R232/R232, and HAQ carrier genotypes. Likewise, to assess the role of psychosocial variables, we will also be using an ANOVA or regression, as appropriate. For secondary analyses, we will not perform any multiple testing corrections for P values.

References

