1. Study Participants: For this study, we will recruit 86 participants. However, not all of those participants will qualify for the study and we estimate that, of the 86, a total of 56 people will qualify for the study. This accounts for a 20% attrition rate, reaching a desired 46 participants based on our power analysis. The 56 participants will be separated into two groups, each consisting of 28 participants. Group 1 will contain individuals with a BMI between 22 and 25. Group 2 will contain obese individuals, defined as a $\text{BMI} \geq 30$ and waist to hip ratio of at least 0.9 in males and at least 0.85 in females. Study participants will be between the ages of 18-35 and in good health.

Recruitment Process: Participants will be recruited in the study under the title, “Pneumonia Vaccine Study.”

Flier - Fliers will be posted on boards and walls at the University of Florida Health Science campus and all affiliated or satellite sites as well as in busy areas with lots of foot traffic within the community (Butler Plaza, Publix, Oaks Mall, etc.).

IDR - If we require more numbers, the IDR will be utilized to contact individuals who fit the criteria for our study. Our co-investigators will be calling each eligible person.

Inclusion Parameters: Alachua county resident

Said yes to recontact for research studies

Obesity diagnosis

Exclusion Parameters: Diabetes, complicated

Drug Abuse

Weight Loss

AIDS

Alcohol abuse

Renal failure

Solid tumor without metastasis

Metastatic cancer

Liver disease

Lymphoma

Leaves 150 possibly eligible participants to contact

ResearchMatch – ResearchMatch allows researchers to search for volunteers who have identified themselves as being interested in participating in research. Interested participants create a “profile”

with basic health information that allows researchers to search for potential participants that meet certain criteria. If a match is identified, the potential participant can be sent details about the study opportunity and can then choose whether to provide their contact information to the researcher. There is an estimated 30 potential participants to contact who are located within 25 miles of UF, between 18 and 35 years of age, have a BMI of 30+, do not smoke, and report no medical conditions.

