To test the primary hypothesis, we will use the Mayo criteria for positivity of 23 titers, with the primary outcome being the number of positives. We shall employ a two-sided ANCOVA, adjusting for age and gender to compare the obese cases to the non-obese controls. Secondarily, we will compare the 23 individual quantitative titers by similar ANCOVA analyses. Other endpoints will be analyzed in a similar manner as tertiary outcomes.

D. Randomization

No randomization will be done in this study.

E. Sample Size

We expect that 23 evaluable obese participants and 23 evaluable normal weight participants will complete the study. To accommodate for 20% attrition rate we will recruit 28 obese participants and 28 normal participants for a total of 56 eligible subjects. Additionally, to accommodate for individuals unable to participate due to exclusion criteria or individuals eliminated post-enrollment due to screening failure (e.g., CBC/CMP abnormalities), we plan to screen an additional 30 subjects. This accounts for a total of 86 individuals screened. Using information from the 2013-2014 MD-PhD study, we compared those with BMI <25 vs. those with BMI > 25. The distribution of Positive titers amongst the 14 was as follows:

BMI	5	6	7	8	9	10	11	12	Total
<25	1	2	0	2	2	1	4	2	14
>25	0	2	3	0	1	1	0	0	7

This should be viewed as conservative, as we will have greater separation of BMI values than the prior study. The actual gain in power cannot be quantified.

F. Technical Support

Under a CTSI voucher, [name] assisted with the statistics and data analysis. [name] co-authored the statistical section with the students. We will use CTRB facilities for blood draw, temporary tissue storage, and basic lab protocols. The laboratory of [name], MD, will be used to perform experimental procedures including the ELISA assays for IgG quantification.

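### The SAP names the Wilcoxon signed-rank test, a paired test, for non-normal comparisons between two unmatched groups; the rank-sum test was probably meant

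*SAP*

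**What the plan says.** The rule is one sentence in the Statistics section of the SAP. It opens with its scope and a normality check: "When comparing between populations (ie. baseline characteristics table), normality was first assessed by the Shapiro-Wilk test". Normal data are "then followed by either an unpaired 2-sided t test"; the alternative is Wilcoxon's "signed-rank test for parametric data or nonparametric data, respectively".

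The design leaves no doubt about what is being compared. The SAP's Study design section states: "This study is a prospective cohort study with two arms". The arms are defined by BMI, plus waist-to-hip ratio for the obese arm. Protocol section 4.A.1 (Study Participants) adds: "The 56 participants will be separated into two groups, each consisting of 28 participants". Protocol section 5.D states: "No randomization will be done in this study". Age and sex are handled by covariate adjustment, the primary ANCOVA "controlling for sex and age", and not by matching. Neither document mentions a rank-sum or Mann-Whitney test, and the protocol's Statistical Methods section names only ANCOVA.

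**The concern.** The signed-rank test is the nonparametric counterpart of the paired t test. It needs one difference per pair, or a single sample. The only natural pairs in this study are the two visits of the same participant, and the sentence is expressly about comparing populations.

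For a non-normal continuous variable in the baseline table, the rule therefore gives either no result (unequal groups) or a P value that depends on which row happens to sit opposite which (equal groups). In a non-randomized comparison, the baseline table is where readers judge whether the groups differ in more than obesity, so its P values should at least be well defined.

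**Working it through.** **1. The plan's own figure, and whether it is touched.** The SAP's Table 1 gives positive-titer counts from the prior study.

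- BMI <25: n = 14, sum 129, mean 129/14 = 9.214, SD 2.326.
- BMI >25: n = 7, sum 52, mean 52/7 = 7.429, SD 1.512.
- Pooled SD = √[(13 × 2.326² + 6 × 1.512²)/19] = 2.104.
- Standardized difference = 1.786/2.104 = 0.849.

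A two-sided unpaired t test at 0.05 with 80% power needs 22.8, so 23 per group, with power 0.804 at 23. This reproduces the stated 23. It rests on the t test, so the choice between signed-rank and rank-sum does not alter it.

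**2. What each test needs.**

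- Signed-rank: dᵢ = xᵢ − yᵢ for each pair i, then the ranks of |dᵢ| summed over dᵢ > 0. This requires equal lengths and a meaningful pairing.
- Rank-sum: U = number of cross-group pairs with x > y, plus half the ties. This requires neither.

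As an illustration only, since these are not baseline data of this trial, Table 1 has 14 and 7 observations. The signed-rank statistic cannot be formed. Rank-sum gives U = 71.5 out of 14 × 7 = 98, P = 0.097, close to the unpaired t test (P = 0.082).

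**3. How often would the groups be equal?** Protocol section 5.E says: "To accommodate for 20% attrition rate we will recruit 28 obese participants and 28 normal participants". Assume independent completion with probability p in each group of 28. Then P(equal) = Σₖ [C(28,k) pᵏ (1−p)²⁸⁻ᵏ]².

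| Assumed completion | P(equal sizes) |
|---|---|
| 80% | 0.133 |
| 23/28 | 0.139 |
| 90% | 0.180 |

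Under these assumptions a completers' table would have unequal groups more than 80% of the time.

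**4. If the groups are equal and the test is run literally.** The documents give no distribution for any baseline variable, so these settings are assumptions: lognormal data, 23 per group, random row order, 10,000 simulated data sets per row, two-sided 0.05. The last column is the share of data sets in which a second random row order changes the signed-rank verdict.

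| Log SD | Log shift | Signed-rank rejects | Rank-sum rejects | Verdict changes |
|---|---|---|---|---|
| 0.5 | 0 | 5.0% | 5.0% | 3.7% |
| 0.5 | 0.3 | 45.6% | 48.7% | 13.2% |
| 0.5 | 0.6 | 95.8% | 97.2% | 2.7% |
| 0.5 | 0.9 | 100% | 100% | 0% |
| 1 | 0 | 5.0% | 4.8% | 4.0% |
| 1 | 0.3 | 14.2% | 15.2% | 8.2% |
| 1 | 0.6 | 43.4% | 48.4% | 14.6% |
| 1 | 0.9 | 76.6% | 82.3% | 11.6% |
| 1.5 | 0 | 4.9% | 5.0% | 4.4% |
| 1.5 | 0.3 | 8.6% | 9.5% | 6.3% |
| 1.5 | 0.6 | 21.4% | 24.7% | 11.4% |
| 1.5 | 0.9 | 42.2% | 48.6% | 15.8% |

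The power loss runs from 0 (100 − 100) to 6.4 percentage points (48.6 − 42.2). A separate run of 4,000 data sets at log SD 1 and shift 0.7 agrees: 54.7% against 60.9%, a loss of 6.2 points, with null rejection of 4.7% against 4.3%. When row order is unrelated to the values, arbitrary pairing adds noise but does not inflate false positives.

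**The case against.** The best defence is that this is a slip of naming that the sentence itself exposes. It speaks of comparing populations and sets the test beside an unpaired t test, so a competent analyst would run rank-sum. With unequal groups the literal instruction fails at once and would be noticed. No inferential result depends on it, and baseline P values do not select covariates, because age and sex are fixed in advance. All of that stands, and it is why the point is minor.

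The sizes above can also be challenged. The SAP does not restrict the baseline table to completers. The protocol plans 28 and 28, and its section 7 (Time and Events) starts the analysis once 56 participants have gone through the study, so equal groups are possible. That also stands: the 13% to 18% is conditional on a completers' table with independent attrition. But equal groups are the case in which the wrong test would run without an error message, so equality is no protection. The lognormal settings are tied to no actual variable and are illustrative only.

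What does not stand is that context makes a correction unnecessary. This sentence is the only instruction for non-normal between-group comparisons, and it names a test that does not fit the design.

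**Conclusion.** The concern holds, at minor severity. The rule is wrong as written for two unmatched groups, and rank-sum was very probably intended. Followed literally, it gives no P value when group sizes differ. With equal groups of 23 it gives a row-order-dependent one, with type I error of 4.9% to 5.0%, power 0 to about 6 points below rank-sum, and a verdict that changes on re-ordering in about 4% of null data sets and 0 to 16% of shifted ones. These sizes rest on the assumed lognormal settings and random row order.

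That the design is unpaired rests on the documents alone. The effect is confined to comparisons under this sentence, in practice the baseline table. The primary ANCOVA, the STING ANOVA, the psychosocial analyses and the 23 per group do not change.

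**What to change.** In the SAP's Statistics section, replace Wilcoxon's signed-rank test with the Wilcoxon rank-sum (Mann-Whitney) test for comparisons between groups. The sentence is in the past tense while the primary analysis is described in the future, so some baseline P values may already exist. The documents show none, so this is a precaution: confirm that any such values came from the rank-sum test, and re-run them if not. The cost is one phrase and a short check of output. No new data are needed, and neither the sample size nor the primary analysis is affected.

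### Protocol and SAP name different primary outcomes, the SAP's fold-change outcome is not reduced to one variable, and its 80% power belongs to a count it never analyses

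*SAP*

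**What the plan says.** **Protocol 5.C (Statistical Methods)** has a single primary variable: "we will use the Mayo criteria for positivity of 23 titers, with the primary outcome being the number of positives". It is compared between groups by a two-sided ANCOVA adjusted for age and gender. The quantitative titers rank lower: "Secondarily, we will compare the 23 individual quantitative titers by similar ANCOVA analyses".

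**SAP, Outcomes**, defines the primary outcome as "Vaccine response as measured by serotype-specific IgG antibody responses against the 23 pneumococcal serotypes". **SAP, Statistics**, continues: "For our primary analysis, we will use an ANCOVA to test for differences in fold change titer levels across groups", controlling for sex and age.

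**SAP, Sample size calculation**, uses a different variable: "The primary outcome measure for the power calculation was the number of positive pneumococcal titers". It states 23 evaluable participants per group at a significance level of 0.05 "for a 2-sided t test at 80% power". The effect comes from Table 1, which is introduced as "The distribution of positive titers amongst the 14".

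**Multiplicity** is mentioned once in the SAP: "For secondary analyses, we will not perform any multiple testing corrections for P values". Nothing is said about the primary analysis.

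Elsewhere the protocol is looser. The primary hypothesis in section 2 (repeated in 5.B) concerns antibody levels before and after vaccination, Specific Aim 1 concerns changes in response, and section 4.F describes the primary outcome as relative differences in immune-marker levels.

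**The concern.** A count of titers that meet a positivity criterion and a ratio of quantitative titers are different variables and can give different answers. A participant who is positive for many serotypes at baseline can score high on the count and still show a small fold change.

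Three things follow.

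- The two documents do not agree on which result decides the primary hypothesis.
- The SAP does not turn 23 fold changes per person into one tested quantity. It gives no averaging rule, scale, joint model, lead serotype or success rule, so the choice could be made after results are seen.
- The stated power does not apply to the analysis named as primary. The documents therefore do not show that 23 per group is enough for fold change.

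There is also a conditional risk to the type I error. If the primary analysis were run as one ANCOVA per serotype at 0.05, the SAP contains no statement that a single nominally significant serotype does not reject the primary null.

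**Working it through.** **Step 1. Reproduce the plan's own figure.** Inputs are the counts in SAP Table 1 (the same table is in Protocol 5.E).

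| Group | n | Sum of counts | Mean | Sum of squares about the mean | SD |
|---|---|---|---|---|---|
| BMI <25 | 14 | 129 | 9.21 | 70.36 | 2.33 |
| BMI >25 | 7 | 52 | 7.43 | 13.71 | 1.51 |

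- Difference in means: 9.214 − 7.429 = 1.786.
- Pooled SD: √[(70.36 + 13.71)/(14 + 7 − 2)] = √(84.07/19) = 2.10.
- Standardised difference: d = 1.786/2.104 = 0.849.
- Two-sided t test, alpha 0.05, n = 23 per group: noncentrality d√(n/2) = 0.849 × √11.5 = 2.88, with critical value 2.015 on 44 degrees of freedom. Power is **80.4%**, and 80% power needs **22.8** per group.

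The plan's 23 per group and 80% are therefore reproduced, and they come from the count of positives.

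**Step 2. How firm is that effect?** With pooled variance, t = 1.83 on 19 degrees of freedom and p = 0.082; the noncentral-t 95% interval for d is −0.11 to 1.78. Without the equal-variance assumption (Welch), p = 0.049. These values are derived from Table 1; neither document states them.

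**Step 3. Power for fold change.** Neither document gives a mean, SD or effect for fold change, so its power cannot be calculated. For a single fold-change variable at 23 per group, the same formula with *assumed* standardised differences gives:

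| Assumed d | Power |
|---|---|
| 0.5 | 38% |
| 0.7 | 64% |
| 1.0 | 91% |

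The smallest d with 80% power is 0.845. The 80% carries over only if fold change happens to have about the same standardised difference as the count.

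**Step 4. Error rate, only if each of the 23 serotypes is tested at 0.05.** With independent tests, the chance of at least one false positive is 1 − 0.95²³ = 0.693. With a common correlation ρ between the test statistics, it is

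1 − ∫ [Φ((c − √ρ·z)/√(1−ρ)) − Φ((−c − √ρ·z)/√(1−ρ))]²³ φ(z) dz, with c = 1.96.

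| ρ (assumed) | 0 | 0.3 | 0.5 | 0.7 | 0.9 | 0.95 | 0.99 |
|---|---|---|---|---|---|---|---|
| At least one false positive | 69% | 58% | 45% | 31% | 16% | 12% | 8% |

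The limit is 5% as ρ approaches 1. A simulation of 20,000 null trials per value of ρ (23 per group, ANCOVA with age and sex) agreed to within 0.01. In the same simulation, one ANCOVA on the mean of the 23 outcomes rejected in 4.7% to 5.3% of trials. The documents give no correlation.

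**The case against.** The strongest reply is that the multiplicity problem is hypothetical. The SAP speaks of one ANCOVA in the singular and limits its waiver of correction to secondary analyses, and both fit a single primary test. That is right, and the error rates in step 4 are conditional for that reason. The established fault is that the variable for that single test is not named.

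It can also be said that missing power information is not evidence of too small a trial, and that the SAP openly labels the count as the outcome used for power. Also correct: the 38%, 64% and 91% rest on assumed effects and do not show underpowering. However, the SAP says that 23 per group gives enough power for the study, while the primary analysis it describes uses another variable.

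The looser wording in Protocol sections 2 and 4.F could be read as background that 5.C makes operational. That is fair, and the main conflict is between 5.C and the SAP. Still, change or fold change fits the hypothesis and Aim 1 better than a count at one visit, so it is not obvious which document should give way. Nothing in either says that the SAP overrides the protocol.

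This is a non-randomised study that the protocol calls a pilot and limits to association. That lowers the stakes. It does not remove the need for an identifiable primary variable once a primary test, an alpha and a power are stated.

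One further point stands. The SAP is dated April 2017 but cites a 2019 publication and is partly in the past tense, so the timing of its text relative to the data is unclear. A correction made after results are known would not restore prespecification.

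**Conclusion.** The concern holds, and the plan must be corrected. Protocol 5.C and the SAP name different primary variables, the SAP's fold-change outcome is not reduced to one tested quantity, and the 80% power belongs to a count that the SAP does not analyse.

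The sample size arithmetic itself is right: 80.4% at 23 per group for d = 0.85, taking the Table 1 effect at face value although it rests on 14 and 7 people. Power for fold change is unknown, not shown to be low. The error rate is 5% under any single prespecified test; the 69% to 8% range applies only to 23 separate tests at 0.05 and depends on an assumed correlation.

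**What to change.** Name one primary variable and one age- and sex-adjusted ANCOVA at two-sided 0.05, identically in both documents. Two choices are workable.

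- **Number of positive titers, as in Protocol 5.C.** This is the simpler choice because it keeps the link to the power calculation. State the visit at which positives are counted, which 5.C does not give, and how baseline positivity is handled, since Aim 1 is about change. Also say what the 14 in the title of Table 1 refers to: it could be the number of titers, but it is also the number of participants with BMI <25. If it is the number of titers, state the assumption that the effect carries over to a count out of 23.
- **One fold-change summary,** for example the mean log fold change over the 23 serotypes. This fits the hypothesis and Aim 1 better. State that the 80% was calculated for the count, and either say that power for this endpoint is unknown or obtain outside variance data to calculate it.

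In either case:

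- align Protocol sections 2, 4.F, 5.B and 5.C and the SAP's Sample size calculation, Outcomes and Statistics sections with the choice;
- label the 23 serotype comparisons secondary and, under the SAP's own rule, unadjusted (adjusting them is optional);
- state that no single unadjusted serotype result rejects the primary null;
- record when the choice was made relative to access to the data, and call it post hoc if results were already known.

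The cost is a few sentences in the SAP and matching wording in the protocol, with no new data and no required change in sample size. The fold-change option adds the work of finding variance data if a power figure is wanted. The small downside is that claims about single serotypes become harder to make.

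### The SAP does not say whether its primary analysis of 23 serotypes is one test or 23, and neither document gives a multiplicity or decision rule for the serotype comparisons

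*SAP*

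**What the plan says.** **SAP.** Under Outcomes, the primary outcome is "Vaccine response as measured by serotype-specific IgG antibody responses against the 23 pneumococcal serotypes". Under Statistics, the primary analysis is an ANCOVA of fold change in titre between the nonobese and obese groups, controlling for sex and age. The significance rule is general: "All hypothesis tests were 2-sided where a P value < 0.05 was considered significant". The section closes with "For secondary analyses, we will not perform any multiple testing corrections for P values"; the analyses it has just called secondary concern STING genotype and psychosocial variables. Nothing is said about multiplicity in the primary analysis.

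**Protocol, section 5.C.** The primary outcome is a single number per participant, the count of titres that are positive by the Mayo criteria, compared by a two-sided ANCOVA adjusted for age and gender. Then: "Secondarily, we will compare the 23 individual quantitative titers by similar ANCOVA analyses". The protocol gives no alpha and no multiplicity rule.

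**Power.** The SAP's sample size section says "The primary outcome measure for the power calculation was the number of positive pneumococcal titers" and that "we expect that 23 evaluable obese participants and 23 evaluable normal weight participants will provide enough power for the study", at alpha 0.05 "for a 2-sided t test at 80% power".

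**The concern.** The primary null (protocol sections 2 and 5.B) is that antibody levels to the vaccine serotypes are identical in the two groups. Neither document says how many serotypes, or which, must differ to reject it. An analyst following the SAP has 23 outcomes, a threshold of 0.05 for every test, and no summary variable or family rule. Running 23 ANCOVAs and reporting those below 0.05 would comply with the text, and a single significant serotype could then be presented as evidence that obesity alters the vaccine response.

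Two things are at stake: the false-positive rate behind the main claim, and whether the stated power belongs to the analysis that will be reported. The sample size was set for the count of positive titres, while the SAP's primary analysis is of fold change.

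**Working it through.** **1. Reproduce the stated sample size.** Input: the prior-study table of positive titres, printed in both documents.

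- BMI < 25: n = 14, sum = 5 + 12 + 16 + 18 + 10 + 44 + 24 = 129, mean 129/14 = 9.214, SD 2.326.
- BMI > 25: n = 7, sum = 12 + 21 + 9 + 10 = 52, mean 52/7 = 7.429, SD 1.512.
- Pooled SD = √[(13 × 2.326² + 6 × 1.512²)/19] = 2.104.
- d = (9.214 − 7.429)/2.104 = 1.786/2.104 = 0.849.
- With 23 per group, noncentrality = 0.849 × √(23/2) = 2.88, 44 df, critical t = 2.015. Power = 80.4%; 23 is the smallest group size that reaches 80%.

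The plan's figure is therefore right for one two-sided t test on the count of positive titres. The table holds no fold-change data, so it gives no power for the SAP's primary analysis.

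**2. Reading A: 23 separate tests at 0.05, no true difference.**

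- Expected false positives = 23 × 0.05 = 1.15, whatever the correlation.
- If independent, P(at least one) = 1 − 0.95²³ = 0.693.
- The titres come from the same people, so correlation is plausible, but the documents give no value. Assuming a common correlation ρ between all pairs, P(at least one) = 1 − ∫[Φ((1.96 − √ρ z)/√(1 − ρ)) − Φ((−1.96 − √ρ z)/√(1 − ρ))]²³ φ(z) dz.

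| Assumed ρ | P(at least one P < 0.05) |
|---|---|
| 0 | 69% |
| 0.3 | 58% |
| 0.5 | 45% |
| 0.7 | 31% |
| 0.8 | 23% |
| 0.9 | 16% |

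Simulated ANCOVAs with 23 per group, adjusted for age and sex (46 − 4 = 42 residual df, 20,000 replicates), gave 69%, 59%, 46%, 31% and 25% at ρ = 0, 0.3, 0.5, 0.7 and 0.8, so small-sample effects do not change the picture.

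**3. Reading B: one ANCOVA pooling all 23 values per person, with no participant effect.** The model treats 23 correlated values as independent. The true variance of the group difference exceeds the assumed variance by a factor of about 1 + 22ρ, so the real false-positive rate is about 2 × [1 − Φ(1.96/√(1 + 22ρ))].

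| Assumed ρ | 1 + 22ρ | 1.96/√(1 + 22ρ) | False-positive rate |
|---|---|---|---|
| 0.3 | 7.6 | 0.711 | 48% |
| 0.5 | 12.0 | 0.566 | 57% |
| 0.7 | 16.4 | 0.484 | 63% |
| 0.9 | 20.8 | 0.430 | 67% |

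**4. Reading C: one scalar per participant, or a mixed model with a participant random effect.** Either gives one test at about 5%. The protocol's count is of this kind. The SAP's analysis text defines neither.

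**The case against.** The strongest reply is that the protocol already has one primary test, on the count, with about 5% error, and makes the serotype comparisons secondary. The SAP also writes of its ANCOVA in the singular. The study calls itself a pilot and limits its conclusions to association, and uncorrected secondary comparisons in such a study are mainly a matter of disclosure. Much of this stands, and it limits the point in four ways.

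- A reader might infer that the primary claim is exposed to a large error rate whichever document governs. It is not: under the protocol's count test it is about 5%. The 16% to 69% applies only if 23 tests are run and any one positive is taken as the finding. Neither document states that rule; equally, neither states any other.
- A reader might infer that the SAP refuses to correct the 23 serotype tests. Its no-correction sentence covers secondary analyses, whereas in the SAP the serotypes are primary. The sentence reaches them only if the protocol's ranking is combined with the SAP's rule. For its own primary outcome the SAP is silent.
- A reader might take a middle correlation and call a false claim likely. Correlation is unknown, and the figure falls below one half at ρ = 0.5 and above.
- A reader might apply d = 0.849 to each serotype at 0.05/23 and quote about 37% power. That d comes from counts of positive titres, and nothing in the documents supports carrying it over to the fold change of a single serotype.

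The singular wording does not settle the matter. With no scalar summary defined, one ANCOVA over all 23 values needs a participant effect to be valid (Reading B), and the SAP specifies none. Nor does either document label the serotype comparisons descriptive.

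**Conclusion.** The gap is real and should be fixed. The SAP's primary analysis is not specified well enough to have a known error rate. It is about 5% with a proper single test. With 23 tests and an any-positive reading it is about 16% to 69% (ρ from 0.9 to 0, equal correlation assumed). With naive pooling it is about 48% to 67% (ρ from 0.3 to 0.9). The protocol's count test is sound on this point, but the 23 secondary comparisons beside it have no adjustment and no rule for interpretation. The 80% power is correct for the count of positive titres and is not evidence of power for the SAP's fold-change analysis.

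The documents do not support saying that 23 separate primary tests are planned, or that correction of them has been ruled out.

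**What to change.** In the SAP Statistics section, with protocol 5.C brought into line:

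1. Name one test at two-sided 0.05 to carry the primary claim, the same in both documents. Either use the ANCOVA on the count of positive titres, which is what was powered, or one mixed model over the 23 log fold changes with a participant random effect and a single obesity coefficient.
2. Report the 23 serotype comparisons as one family with Holm or false-discovery-rate adjusted P values, or label them descriptive and make no significance claims from them.
3. State that the no-correction sentence does not cover these 23 comparisons.
4. State that the 80% power refers to the test on the count only. If the mixed model is chosen as primary, its power has to be worked out separately, because the documents hold no fold-change variance or correlation.

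The cost is wording and a few lines of analysis code. The price is that claims about individual serotypes become harder to make.
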